9.2.3.1 Adverse Events

9.2.3.1.1 Time Period and Frequency for Collecting and Reporting Safety Event Information

9.2.3.1.1.1 Disease-related Events

Disease-related events are defined in [Appendix 4](#).

The investigator is responsible for ensuring that all disease-related events observed by the investigator or reported by the subject that occur after the first dose of investigational product(s) through the safety follow-up are reported using the Event CRF.

Disease-related events assessed by the investigator to be more severe than expected and/or related to the investigational product(s)/study treatment/protocol-required therapies, and determined to be serious, must be reported on the Event CRF as serious adverse events.

Disease-related events pre-defined for this study include joint pain, joint stiffness, joint swelling, worsening of rheumatoid arthritis.

9.2.3.1.1.2 Adverse Events

The adverse event grading scale to be used for this study will be the Common Terminology Criteria for Adverse Events (CTCAE) and is described in [Appendix 4](#).

The investigator is responsible for ensuring that all adverse events observed by the investigator or reported by the subject that occur after first dose of investigational product through the safety follow-up are reported using the Event CRF.

9.2.3.1.1.3 Serious Adverse Events

The investigator is responsible for ensuring that all serious adverse events observed by the investigator or reported by the subject that occur after signing of the informed consent through the safety follow-up are reported using the Event CRF.

All serious adverse events will be collected, recorded and reported to the sponsor or designee within 24 hours, as indicated in [Appendix 4](#). The investigator will submit any updated serious adverse event data to the sponsor within 24 hours of it being available.

The criteria for grade 4 in the CTCAE grading scale differs from the regulatory criteria for serious adverse events. It is left to the investigator's judgment to report these grade 4 abnormalities as serious adverse events.

9.2.3.1.1.4 Serious Adverse Events After the Protocol-required Reporting Period

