| 
• Disease-related events are events (serious or non-serious) anticipated to occur in the study population due to the underlying disease. See Section 9.2.3.1.1.1 for the list of disease-related events.• Disease-related events that would qualify as an adverse event or serious adverse event:
○ An event based on the underlying disease that is worse than expected as assessed by the investigator for the subject's condition or if the investigator believes there is a causal relationship between the investigational product(s)/study treatment/protocol-required therapies and disease worsening, this must be reported as an adverse event or serious adverse event.• Disease-related events that do not qualify as adverse events or serious adverse events:
○ An event which is part of the normal course of disease under study (eg, disease progression in oncology or hospitalization due to disease progression) is to be reported as a disease-related event. |

Definition of Adverse Event

| Adverse Event Definition |
|---|
| 
• An adverse event is any untoward medical occurrence in a clinical study subject irrespective of a causal relationship with the study treatment.• Note: An adverse event can therefore be any unfavorable and unintended sign (including an abnormal laboratory finding), symptom, or disease (new or exacerbated) temporally associated with the use of a treatment, combination product, medical device or procedure. |

| Events Meeting the Adverse Event Definition |
|--|
| 
• Any abnormal laboratory test results (hematology, clinical chemistry, or urinalysis) or other safety assessments (eg, electrocardiogram [ECG], radiological scans, vital signs measurements), including those that worsen from baseline, that are considered clinically significant in the medical and scientific judgment of the investigator (ie, not related to progression of underlying disease).• Exacerbation of a chronic or intermittent pre-existing condition including either an increase in frequency and/or intensity of the condition.• New conditions detected or diagnosed after study treatment administration even though it may have been present before the start of the study.• Signs, symptoms, or the clinical sequelae of a suspected drug-drug interaction. |

Approved

Events Meeting the Adverse Event Definition

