| 
• When an adverse event, disease-related event or serious adverse event occurs, it is the responsibility of the investigator to review all documentation (eg, hospital progress notes, laboratory, and diagnostics reports) related to the event.• The investigator will then record all relevant adverse event/disease-related event/serious adverse event information in the Event case report form (CRF).
○ Additionally, the investigator is required to report a fatal disease-related event on the Event CRF.• The investigator must assign the following adverse event attributes:
○ Adverse event diagnosis or syndrome(s), if known (if not known, signs or symptoms);○ Dates of onset and resolution (if resolved);○ Severity (or toxicity defined below);○ Assessment of relatedness to investigational product, other protocol-required therapies; and○ Action taken.• If the severity of an adverse event changes from the date of onset to the date of resolution, record as a single event with the worst severity on the Event CRF.• It is not acceptable for the investigator to send photocopies of the subject's medical records to the sponsor in lieu of completion of the Event CRF page. |

Approved

Adverse Event, Disease-related Event (if applicable) and Serious Adverse Event Recording

- If specifically requested, the investigator may need to provide additional follow-up information, such as discharge summaries, medical records, or extracts from the medical records. In this case, all subject identifiers, with the exception of the subject number, will be blinded on the copies of the medical records before submission to Amgen.
- The investigator will attempt to establish a diagnosis of the event based on signs, symptoms, and/or other clinical information. In such cases, the diagnosis (not the individual signs/symptoms) will be documented as the adverse event/serious adverse event.

Evaluating Adverse Events and Serious Adverse Events

Assessment of Severity

The investigator will make an assessment of severity for each adverse event and serious adverse event reported during the study. The assessment of severity will be based on:

The **Common Terminology Criteria for Adverse Events (CTCAE)**, version 4.0 which is available at the following location:
http://ctep.cancer.gov/protocolDevelopment/electronic_applications/ctc.htm

Assessment of Causality

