A positive ACR 20 response is defined as at least 20% improvement from baseline in both TJC and SJC, and a 20% improvement or more in at least 3 of the following 5 criteria: physician global assessment of disease activity (PGA, 0-100 scale), subject (patient) global assessment of disease activity (SGA, 0-100 scale), patient global assessment of joint pain (0-100 visual analog scale), subject self-assessment of disability (Health Assessment Questionnaire, HAQ-DI), and acute phase reactant: C-Reactive Protein (CRP).

ACR 50

A positive ACR 50 response is defined by using the definition of ACR 20 response described above but requiring at least 50% improvement.

ACR 70

A positive ACR 70 response is defined by using the definition of ACR 20 response described above but requiring at least 70% improvement.

DAS28-CRP

The DAS28-CRP is a composite score that is based on a 28-joint count (using TJC28 and SJC28), CRP (in mg/L), and SGA. [REDACTED]

DAS28-ESR

The DAS28-ESR is a composite score that is based on a 28-joint count (using TJC28 and SJC28), ESR (in mm/hour), and SGA.

Incidents of Interest

Incidents of interest such as selected adverse events or intolerable PD levels will be identified after safety data is collected and before each DLRM convenes. Number of incidents of interest according to treatment received will be used in the BLRM for the DLRM analysis to aid decision in DLRMs. The incidents of interest will be listed in the separate document of analysis plan for DLRM. The list can be updated to include emerging incidents as data get collected.

Adverse Event

This includes all adverse events /serious adverse events and disease-related events as identified on the Adverse Events eCRF.

Treatment Emergent Adverse Event (TEAE)

A treatment emergent adverse event is any adverse event (including disease-related events) starting on or after the first dose of investigational product (as determined by the flag indicating if the adverse event started prior to the first dose or not on the Adverse Events eCRF) and up to and including 42 days after the end of investigational product or the End of Study date, whichever is earlier.

Disease Related Event

Events anticipated to occur in the study population due to the underlying disease. Protocol lists joint pain, joint stiffness, joint swelling, and worsening of

rheumatoid arthritis as disease related events. These will be identified on the Adverse Events eCRF.

QTcB

QTcB by Bazett's formula will be derived as:

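### The SAP counts all disease-related events as TEAEs, although protocol Appendix 4 excludes normal-course ones from AEs, and no planned table clearly gives AE-only subject incidence

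*SAP*

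**What the plan says.** SAP 5.3 defines the term Adverse Event broadly: "This includes all adverse events /serious adverse events and disease-related events as identified on the Adverse Events eCRF". The TEAE definition builds on it: "A treatment emergent adverse event is any adverse event (including disease-related events) starting on or after the first dose of investigational product". The window closes 42 days after the end of investigational product or at the end of study, whichever is earlier. TEAEs are the first-listed phase 1b primary endpoint (protocol 4.1, SAP 2.1).

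Protocol Appendix 4 divides disease-related events in two. One kind becomes an AE or SAE: "An event based on the underlying disease that is worse than expected as assessed by the investigator", or one the investigator believes was caused by treatment. The other kind falls under the label "Disease-related events that do not qualify as adverse events or serious adverse events", described as "An event which is part of the normal course of disease under study". Protocol 9.2.3.1.1.1 lists the terms: "Disease-related events pre-defined for this study include joint pain, joint stiffness, joint swelling, worsening of rheumatoid arthritis".

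SAP 9.6.2 plans subject-incidence tables for all TEAEs, serious TEAEs, treatment-related events, withdrawals and fatal events, tables by worst grade, and an overall summary by grade and type. It also plans separate disease-related summaries, for all treatment-emergent events and for fatal ones. None is planned for serious disease-related events.

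**The concern.** The SAP's set of adverse events is wider than the protocol's. Under Appendix 4, an ordinary episode of joint stiffness in a patient with active RA is a disease-related event and not an AE. Under SAP 5.3 it is a TEAE, so it counts towards the primary endpoint.

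What is at stake is how the primary safety tables read. From the any-TEAE row a reader cannot tell how many subjects had an event that meets the protocol's AE definition and how many had only ordinary RA symptoms. Cohorts have 6 or 12 subjects on AMG 592, so one subject moves a cohort's incidence by 1/6 (about 17 percentage points) or 1/12 (about 8 points). Joint symptoms can be expected on placebo too, which could blur the descriptive contrast between arms.

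**Working it through.** **1. Which tables are touched.**
- Any-TEAE row, affected SOC totals, and joint and RA terms: touched, because SAP 5.3 puts normal-course events into TEAE and SAP 9.6.2 states no exclusion.
- Serious-TEAE table: touched only for serious events in the normal course of disease. Protocol 9.2.3.1.1.1 already covers disease-related events that are more severe than expected or related: those "and determined to be serious, must be reported on the Event CRF as serious adverse events". No serious disease-related table exists to read against this one.
- Tables by grade: touched only if normal-course events are graded. Appendix 4 requires grading for AEs and SAEs: "The investigator will make an assessment of severity for each adverse event and serious adverse event reported during the study".
- Treatment-related tables: not affected, because a disease-related event believed related is an AE under Appendix 4.
- Rows for other terms, such as injection-site erythema: not affected.

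**2. The plan's own figures.** The sample-size sections give the chance of at least one subject with an adverse event, 1-(1-p)^n. For n = 6 and p = 25%, 1-0.75^6 = 82.2% (stated 82%). For n = 12 and p = 20%, 1-0.80^12 = 93.1% (stated 93%). For n = 36 and p = 5%, 1-0.95^36 = 84.2% (stated 84%). These reproduce and are not in dispute. The documents give no figure for disease-related events.

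**3. Can the AE-only count be recovered?** Divide the subjects with any TEAE into three groups:
- a: qualifying AEs only, and not in the disease-related table;
- b: in the disease-related table and also with a qualifying AE;
- d: normal-course disease-related events only.

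The any-TEAE total is U = a + b + d. The disease-related total is D = b + d. The AE-only count is A = a + b = U - d. Since d can be anything from 0 to D, U-D ≤ A ≤ U. Totals alone give nothing tighter.

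Other rows can raise the lower end. Let M be the largest count in any row that can hold only AEs, such as a non-joint SOC or the treatment-related total. Then max(U-D, M) ≤ A ≤ U.

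**4. Illustrations.** All values of U, D and M are assumed.

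| n | U | D | M | AE-only count | Incidence |
|---|---|---|---|---|---|
| 6 | 5 | 2 | not used | 3 to 5 | 50% to 83% |
| 6 | 5 | 2 | 4 | 4 to 5 | 67% to 83% |
| 12 | 9 | 5 | not used | 4 to 9 | 33% to 75% |
| 12 | 9 | 5 | 6 | 6 to 9 | 50% to 75% |
| 12 | 9 | 5 | 8 | 8 to 9 | 67% to 75% |
| 36 | 27 | 9 | not used | 18 to 27 | 50% to 75% |
| 36 | 27 | 9 | 22 | 22 to 27 | 61% to 75% |
| 36 | 27 | 9 | 25 | 25 to 27 | 69% to 75% |

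The range is wide from totals alone and can become narrow once the other rows are read. For serious events no D is planned, so subtraction cannot even start.

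**The case against.** The strongest reply is that the pooling is a legitimate choice. Appendix 4 tells investigators what to record and does not define TEAE; nor does the rest of the protocol. Protocol 10.3.2.3.2 names both event types in its heading, so including disease-related events in its tables is a possible reading. SAP Appendix F logs the definition as a move to the sponsor's standard. Pooling also avoids dependence on each investigator's judgement of what is worse than expected, which is conservative for a safety endpoint. This stands, and it is why the pooled tables should stay. It does not supply the count under the protocol's own AE definition.

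A second reply is that SAP 9.6.2 reports disease-related events separately, SAP 9.6.1 names them as their own item, and the overall summary is by type. So these events are visible. But a pooled total and a disease-related total do not yield the AE-only total, and type is undefined. If separately means that disease-related events are kept out of the AE tables, that contradicts SAP 5.3 and should be stated.

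A reader might infer that the pooling hides the worsening arthritis reported in protocol 3.2.5. The documents do not support that: those events were deemed related, so they are AEs under Appendix 4 and appear in the unaffected treatment-related tables. Nor do the documents support an effect on dose decisions. Those rest on the dose level reviews, with their own analysis plan and incidents of interest, and on protocol Table 7-1.

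**Conclusion.** The conflict between SAP 5.3 and protocol Appendix 4 is in the text and widens the phase 1b primary-endpoint count. It reaches the any-TEAE and serious-TEAE rows and the joint and RA rows. From totals alone, AE-only subject incidence is bounded only by U-D to U. No test is affected, because the analysis is descriptive.

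The size cannot be stated. Every U, D and M above is an assumption, and using M assumes that normal-course events stay within joint and RA terms. A reader might take 33% to 75% as an expected distortion; it only illustrates the bound, and the actual gap may be small. The documents likewise do not support calling the pooling accidental or undisclosed. SAP Section 10 does not list it, but whether an entry is owed there is arguable, since the protocol never defines TEAE. This is a cheap improvement of low to moderate priority.

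**What to change.** Keep the pooled tables. In SAP 9.6.2 add subject-incidence tables of TEAEs and serious TEAEs that exclude records identified on the eCRF only as disease-related events. Keep every event that the investigator reported as an AE or SAE because it was worse than expected or related.

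First confirm how the eCRF identifier is used. If it marks qualifying and normal-course events alike, a simple filter will not work. The event attributes listed in Appendix 4 include relatedness but no field for worse than expected, so the SAP would then have to say how the split is made.

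Two clarifications can go in at the same time: define type in the overall summary, and mention the pooled definition in SAP Section 10.

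The cost is some SAP wording, one check of the eCRF and one or two extra tables; if the identifier separates the two kinds of event, no new data are needed. The drawback is that the added tables depend on the investigator's classification of an event as an AE or a disease-related event, which may vary by site. Protocol 3.2.5 notes that most of the related worsening-arthritis events came from a single site. The new tables should therefore be read beside the pooled ones and not replace them.

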5.4 Demographic and Characteristics

Age

Age in years at randomization, which is collected **in** the eCRF.

RA disease duration

Number of years from the date of diagnosis of RA (**collected in medical history eCRF**) to the date of Study Day 1 in the current study period.

Time on methotrexate

Number of weeks from the date of initial prescription of methotrexate to the date of Study Day 1 in the current study period.

Methotrexate dose

Average weekly total methotrexate dose in mg during the screening period.

Prior and Concomitant medications

Prior medication is defined as any medication that with start date prior to the first dose date of study drug. Concomitant medication is defined as any medication with start date prior to the first dose date of study drug but which continued to be taken after the first dose of study drug or any medication with start date on or after the first dose date and up to and including 42 days after the last dose date.

6. Analysis Sets

6.1 Phase 1b

Subjects will be analyzed according to the actual treatment received.

6.1.1 Safety Analysis Set

The safety analysis set for phase 1b consists of all subjects who received at least 1 dose of investigational product. The safety analysis set will be used for the phase 1b analyses unless otherwise specified.

[figure not shown]
6.1.2 Pharmacokinetic/Pharmacodynamic Analyses Set(s)

6.1.2.1 Pharmacokinetic Concentration Analysis Set

The PK concentration analysis set for phase 1b consists of all subjects who have received at least one dose of AMG 592 and have at least one quantifiable PK sample collected.

6.1.2.2 Pharmacokinetic Parameter Analysis Set

The PK parameter analysis set for phase 1b consists of all subjects who have received at least one dose of AMG 592 and for whom at least one PK parameter is adequately estimated.

7. Planned Analyses

7.1 Interim Analysis and Early Stopping Guidelines

[figure not shown]
Phase 1b

There is no formal interim analysis for phase 1b.

DLRM analyses will be conducted after the last subject in each cohort completes the week 4 visit, with an exception for cohorts 2 and 3 where the analysis will be conducted after the last subject enrolled in both cohorts completes the week 4 visit.

The study statistician will perform the analyses and provide the result to the DLRM before the meeting convenes. The DLRM members will conduct aggregated review of safety data and the analyses results to make dosing decisions.

[figure not shown]
The scope of the DLRM analyses includes a Bayesian logistic regression model (BLRM) [REDACTED], where posterior probabilities of incident of interest at each dose level will be summarized and reported. In addition, safety data including demographics, medical history, concomitant therapies, adverse events, electrocardiograms, vital signs, laboratory results, and emerging pharmacokinetic and pharmacodynamics data will be listed or plotted. For a complete list of planned outputs including subject level listings and line plots refer to a separate SAP for DLRM.

7.2 Primary Analysis

7.2.1 Phase 1b

The primary analysis will be done after all subjects have had the opportunity to complete the study and performed the safety follow-up.

8. Data Screening and Acceptance

8.1 General Principles

The objective of the data screening is to assess the quantity, quality, and statistical characteristics of the data relative to the requirements of the planned analyses.

8.2 Data Handling and Electronic Transfer of Data

The Amgen Global Study Operations-Data Management (GSO-DM) department will provide all data to be used in the planned analyses. The database will be subject to edit checks outlined in the Data Management Plan (DMP). See details of this section in the DMP.

8.3 Handling of Missing and Incomplete Data

If there are missing or incomplete start and/or stop dates for **adverse events, prior and concomitant medications, or medical history events and the analysis requires complete dates, then dates are imputed as per the imputation rules provided in Appendix A. No imputation is performed if there is no need of these dates for the analysis.**

Laboratory measurements that are below the lower quantification limits will be considered equal to the lower limit of quantification for all analyses unless explicitly noted otherwise.

[REDACTED]

Subject may have missing study endpoint data for a variety of causes. In general, data may be missing due to a subject's early withdrawal from study, a missed visit, or inability to evaluate an endpoint at a particular timepoint. The general procedures outlined below describe what will be done when endpoint data is missing.

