9.7.3 Analyses of Health Economic Endpoints

Not applicable for the study

10. Changes from Protocol-specified Analyses

ECG listing as planned in the protocol will not be provided because only critical data listings will be included in the CSR and summary tables planned for ECG data will be adequate to identify significant changes (if any) in ECG data.

11. Literature Citations / References

12. Prioritization of Analyses

There is no prioritization of analyses.

13. Data Not Covered by This Plan

Exploratory data not included in this plan may be analyzed at a later date or may be analyzed by a different Amgen Department.

14. Appendices

Appendix A. Technical Detail and Supplemental Information Regarding Statistical Procedures and Programs

Imputation Rules for Partial or Missing Stop Dates

If the month and year are present, impute the last day of the month. If only the year is present, impute December 31 of that year. If the stop date is entirely missing, assume the event or medication is ongoing and do not impute.

Imputation Rules for Partial or Missing Start Dates

		Stop Date							
		Complete: yyyymmdd		Partial: yyyymm		Partial: yyyy		Missing	
Start Date		<1 st Dose	≥1 st Dose	<1 st Dose yyyymm	≥1 st Dose yyyymm	<1 st Dose yyyy	≥1 st Dose yyyy		
Partial: yyyymm	=1 st Dose yyyymm	2	1	2	1	N/A	1	1	
	≠ 1 st Dose yyyymm		2		2	2	2	2	
Partial: YYYY	=1 st Dose yyyy	3	1	3	1	N/A	1	1	
	≠ 1 st Dose yyyy		3		3	3	3	3	
Missing		4	1	4	1	4	1	1	

[figure not shown]
1 = Impute the date of first dose

[figure not shown]
2 = Impute the first day of the month

[figure not shown]
3 = Impute January 1 of the year

[figure not shown]
4 = Impute January 1 of the stop year

[figure not shown]

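### Appendix A rule 1 can set RA duration or time on methotrexate to 0 when the start date is missing, or when a methotrexate start is known only to the first-dose year

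*SAP*

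**What the plan says.** SAP 8.3 uses one set of date rules for three kinds of record: adverse events, "prior and concomitant medications, or medical history events and the analysis requires complete dates, then dates are imputed as per the imputation rules" given in SAP Appendix A.

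The Appendix A start-date table is read by how much of the start date is known and by the stop date. Two of its codes matter here: "1 = Impute the date of first dose" and "2 = Impute the first day of the month". Code 1 appears for a wholly missing start, and for a start known only to the first-dose year, in every column where the stop date is on or after first dose and in the column where it is missing. For stop dates the appendix adds: "If the stop date is entirely missing, assume the event or medication is ongoing and do not impute".

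SAP 5.4 measures RA disease duration in years from the diagnosis date, "collected in medical history eCRF", to Study Day 1. Time on methotrexate is defined as: "Number of weeks from the date of initial prescription of methotrexate to the date of Study Day 1". No source is named for that prescription date. SAP 5.2.1 makes Study Day 1 the first dosing day, and SAP 9.4.2 summarises both durations as continuous variables.

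Protocol 6.1, criterion 105, requires at least 12 weeks of methotrexate before day 1.

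**The concern.** Taking first dose as the start is a cautious default for an adverse event of unknown onset, because it keeps the event treatment-emergent. It does not suit a diagnosis or background drug that the entry criteria place before Day 1. There it picks the one date that makes the duration exactly 0.

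The records concerned would normally fall in the code 1 columns. Protocol 3.2.1 describes RA as incurable and chronic, so an RA history entry would usually have no stop date. Protocol 7.8.2.1 keeps methotrexate stable through the treatment period and allows changes only afterwards, so the current methotrexate record has either no stop date or one after first dose.

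At stake is the description of the inadequate-responder population. A stated rule could put an impossible minimum into the time-on-methotrexate row and pull down the mean of either row, with no sign to the reader that the value was imputed.

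**Working it through.** The documents give no figure for this point, so there is none to reproduce. The check applies the table to the two definitions.

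**Inputs**
- Code 1: start = date of first dose (SAP Appendix A).
- Study Day 1 = date of first dose (SAP 5.2.1).
- Duration = Study Day 1 minus start date (SAP 5.4).
- Minimum true methotrexate time = 12 weeks = 84 days (Protocol 6.1, criterion 105).
- Subjects on AMG 592: 6 in each of cohorts 1 and 4, 12 in each of cohorts 2 and 3, 36 in all (Protocol 10.1.1).

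**Step 1: the table, for a stop date that is missing or on or after first dose**

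| Start date known | Code | Duration obtained |
|---|---|---|
| Nothing | 1 | 0 |
| Year only, equal to first-dose year | 1 | 0 |
| Year only, another year | 3 (1 January) | not 0 |
| Month known, not the first-dose month | 2 (first of month) | not 0 |

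Under code 1, duration = first dose minus first dose = 0 years or 0 weeks.

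**Step 2: do the visible safeguards stop it?** Appendix A withholds an imputed start only if it falls after the stop date, so it does not act when the stop is missing or on or after first dose. SAP 8.3.1 rules out imputation for endpoints, but these two variables are baseline characteristics.

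**Step 3: effect of one wholly missing methotrexate start.** The error is the whole true time, at least 12 weeks. The fall in the group mean is at least 12/n:
- n = 6: 12/6 = 2.0 weeks
- n = 12: 12/12 = 1.0 week
- n = 36 pooled: 12/36 = 0.33 weeks

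The reported minimum becomes 0 in each case.

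**Step 4: effect of one wholly missing RA diagnosis date.** The documents give no true duration D, so assume 2, 10 or 20 years. The fall in the mean is D/n:
- n = 6: 0.33, 1.67 or 3.33 years
- n = 12: 0.17, 0.83 or 1.67 years
- n = 36: 0.06, 0.28 or 0.56 years

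**Step 5: methotrexate start known only to the first-dose year.** The 12 weeks must fit inside the calendar year, so this needs a first dose no earlier than 1 January + 84 days = 26 March (non-leap year). Two assumed first-dose dates show the size:
- 1 July: 181 days from 1 January, 181/7 = 25.9 weeks. The true time is 12 to 25.9 weeks, and rule 1 errs by all of it. Using 1 January errs by 0 to 25.9 − 12 = 13.9 weeks.
- 1 December: 334/7 = 47.7 weeks. Rule 1 errs by 12 to 47.7 weeks. Using 1 January errs by 0 to 47.7 − 12 = 35.7 weeks.

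With 1 January the derived time is never below 12 weeks for a subject who meets criterion 105.

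**Step 6: methotrexate start known to the month.** No month exceeds 31 days, so a start at least 84 days before Day 1 is always in an earlier calendar month. Code 2 then applies, and the error is at most 30 days (30/7 = 4.3 weeks). This case needs no change.

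**The case against.** The strongest objection is that such records may never arise. Protocol 7.8.1 asks for the complete RA therapy history with start dates, and Protocol 9.2.1.3 takes RA history back to the original diagnosis. Criterion 105 cannot be confirmed without knowing that methotrexate began at least 12 weeks earlier, and Protocol section 6 allows no waivers. SAP 8.2 adds edit checks under a data management plan that is not among the documents. A subject with several methotrexate records may also have an earlier, dated one that supplies the initial prescription date. All of this stands, and it limits how often the rule would act. It does not change what the rule does when it acts.

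Applicability is also partly inferred. If the diagnosis or prescription date sits in a dedicated field, the table may not govern it. This stands for methotrexate, whose source SAP 5.4 does not name. It is weaker for RA, where the medical history eCRF is named. Parts of SAP 8.3 and 8.3.1 are redacted, so an unseen exception cannot be excluded. None is visible.

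A reader might go further in three ways that the documents do not support.
- **The prior RA medication row is wrong too.** Because "Prior medication is defined as any medication that with start date prior to the first dose date of study drug", while concomitant use includes "any medication with start date on or after the first dose date", a drug whose start is imputed to first dose would count as concomitant only. Whether a subject then leaves the row depends on its layout, on the number of records per subject and on what the CRF shows about use before first dose. The documents show none of these.
- **A year-only RA diagnosis in the first-dose year is a comparable error.** The true duration there is under one year, and no criterion makes a value near 0 impossible. Rule 1 and 1 January have the same outer bound of error (0.50 years for a first dose on 1 July, 0.91 for 1 December). The choice is close to a preference.
- **Only ongoing records are affected.** The table also gives code 1 when the stop date is on or after first dose.

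**Conclusion.** The point holds as a narrow defect in a stated rule. Read as written, Appendix A gives 0 for RA duration or time on methotrexate when the start date is wholly missing, and for methotrexate also when it is known only to the first-dose year, provided the stop date is missing or on or after first dose. Zero weeks on methotrexate contradicts criterion 105.

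Per wholly missing methotrexate start, the mean falls by at least 2.0, 1.0 or 0.33 weeks for n = 6, 12 or 36. The RA figures rest on assumed durations. The conclusion also assumes that both dates are treated as start dates under Appendix A and that no redacted text exempts them. The number of affected records is not given and is probably small.

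It would be wrong to infer any threat to the trial's conclusions. Phase 1b has no pre-specified covariates or subgroups (SAP 4.1.1 and 4.2.1) and its primary endpoint is descriptive safety (SAP 9.6.1). No safety result, sample size or dosing decision depends on these rows. The change is optional.

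**What to change.** Add to SAP Appendix A:
- Rule 1 is not used to derive RA duration or time on methotrexate.
- A wholly missing RA diagnosis date or methotrexate start date stays missing, and each row reports the number of subjects with data.
- For a methotrexate start known only to the first-dose year, use 1 January of that year or leave the duration missing.

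Keep rule 1 for adverse events. It would also help to name the source of the initial methotrexate prescription date in SAP 5.4.

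The cost is a few lines of text and a small programming change, with no new data. The downside is a slightly smaller n in two baseline rows. The change is best made before database lock, so that the handling is not chosen after a 0-week value has appeared.
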